5.3 Screening Failures

Patients who signed the ICF but were found not eligible for the study prior to receiving study treatment are defined as screening failures.

For these patients, only limited information will be collected in the electronic case report form (eCRF):

- Informed consent
- Demographics
- Inclusion/exclusion criteria
- Serious adverse event (SAE) and/or death occurring during the Screening Period
- Screen fail (documenting primary reason for screen failure)

5.4 Re-screening Procedures

A patient who did not meet the eligibility criteria (screen failure) may be considered for re-screening. Decision for re-screening must be confirmed by the Sponsor/Medical monitor. A re-screened patient should be assigned a new patient number.

Participants who are rescreened are required to sign a new ICF.

5.5 Discontinuation

The reason for discontinuation, whether it is from study treatment or from study, and the date of discontinuation will be collected for all patients.

Note: Once discontinued from the study for any reason, patients are not permitted to be re-enrolled.

5.5.1 Discontinuation from Study Treatment

A patient may be discontinued from the study treatment for any of the following reasons:

- Disease Progression
- Adverse events
- Patient decision

- Physician decision
- Major protocol deviation
- Lost to follow-up
- Study termination by the Sponsor

A patient must discontinue from the study drug for any of the following reasons:

- Pregnancy
- Death

The reason(s) patients initiate subsequent anti-lymphoma therapy should be captured.

IMPORTANT: Study treatment discontinuation is not equivalent to discontinuation from the study. Patients discontinuing the study treatment will be asked to perform an EOT visit ([Section 4.2.4](#)) and continue with the Follow-up period ([Section 4.2.5](#)) as per protocol.

The investigational site should make every effort to complete follow-up per protocol. If patients are unable to return to the site, patient status, including but not limited to survival status, may be obtained by site staff via phone, email, or mail.

5.5.2 Discontinuation from the Study

A patient may be discontinued from the study for any of the following reasons:

- Study completion
- Withdrawal of consent
- Physician decision
- Lost to follow-up
- Study termination by the Sponsor
- Death

If a patient withdraws informed consent for study participation, no additional study data will be collected.

The Sponsor may continue to use previously collected medical research data prior to the withdrawal consistent with the original authorization. If a patient withdraws from the study, he/she may request destruction of any samples taken and not tested, and the investigator must document this in the site study records.

The study may be terminated at any time, for any reason, by the Sponsor. Patients still receiving study treatment should have an EOT visit as described in [Section 4.2.4](#) and Schedule of Events (SoE) ([Table 1](#) or [Table 2](#)).

5.5.3 Lost to Follow-Up

Patients who fail to return for protocol follow-up are to be contacted by the investigative site. Following a minimum of two documented unsuccessful telephone calls, the investigative site should send a registered letter to the patient in a final attempt to ensure protocol compliance.

5.5.4 Patient Replacements

Any patient who is randomized will not be replaced.

6 Study Treatment

6.1 Study Drugs

Loncastuximab tesirine is an investigational medicinal product for this trial. It will be supplied by the study sponsor. Idelalisib is the comparator regimen in the study. Idelalisib will be supplied by the Sponsor when required by applicable local laws and regulations.

6.1.1 Loncastuximab tesirine

Loncastuximab tesirine will be provided as a lyophilized white to off-white powder in glass vials (10 mg loncastuximab tesirine per vial) and stored at 2-8°C. The lyophilized loncastuximab tesirine is formulated in 20 mM histidine, 175 mM sucrose, and 0.02% polysorbate 20, at pH 6.0. Prior to use, this study drug is reconstituted with 2.2 mL of Sterile Water for Injection to deliver 2.0 mL at a concentration of 5 mg/mL. Sterile Water for Injection is to be provided by study sites. See the Pharmacy Manual for additional details on dose handling and administration.

6.1.2 Idelalisib

Idelalisib tablets are for oral administration. Each tablet contains either 100 mg or 150 mg of idelalisib with the following inactive ingredients: microcrystalline cellulose, hydroxypropyl cellulose, croscarmellose sodium, sodium starch glycolate, magnesium stearate, and a tablet coating. The tablet coating consists of polyethylene glycol, talc, polyvinyl alcohol, and titanium dioxide and of FD&C Yellow #6/Sunset Yellow FCF Aluminum Lake (for the 100 mg tablet) and red iron oxide (for the 150 mg tablet). See the Pharmacy Manual/ idelalisib Prescribing Information/SmPC for additional details on dose handling and administration.

6.2 Management of Clinical Supplies

The investigator or designee must confirm appropriate temperature conditions have been maintained for study drug(s) received and any discrepancies are reported as instructed in the pharmacy manual.

Study drug(s) must be stored in a secure, monitored (manual or automated) area in accordance with the storage conditions specified in the pharmacy manual with access limited to authorized site staff.

The investigator or designee is responsible for study drug accountability, reconciliation, and record maintenance (ie, receipt, reconciliation, and final disposition records).

Detailed instructions regarding study treatment shipment, handling, storage, preparation, administration, and final disposition of unused study treatment are included in the study pharmacy manual and in the prescribing information or SmPC for idelalisib.

6.2.1 Packaging and Storage

The study drugs will be supplied by the Sponsor through the designated packaging, labeling, and distribution center.

Once the package arrives at the study site, the receiving site pharmacy will complete the procedures listed in the pharmacy manual to acknowledge receipt.

Study drugs must be stored according to the pharmacy manual/prescribing information or SmPC, in a secure area.

Loncastuximab tesirine will be provided as a refrigerated lyophilized formulation, and stored at 2-8°C. Loncastuximab tesirine should be stored in the original box to protect from long-term exposure to light. Light protection is not required for dose preparation and during administration of the diluted drug in the IV bag.

Refer to the IB (loncastuximab tesirine), prescribing information or SmPC (idelalisib), and pharmacy manual for storage instructions.

6.2.2 Preparation and Administration

Loncastuximab tesirine

Loncastuximab tesirine solution at the concentration of 5 mg/mL will be the basis for the preparation of the infusion solution. The amount of the product to be diluted will depend on the dose level and the body mass of the patient. The weight of the patient at C1 D1 can be used for calculating the dose. If the patient's weight measured on subsequent dosing days has changed by 10% or more compared to C1 D1, then the dose should be recalculated. Additional details are included in the pharmacy manual.

Administration of loncastuximab tesirine will be performed by the Investigator or a qualified designee according to the pharmacy manual.

Variations in infusion times due to minor differences in IV bag overfill/underfill and the institution's procedure for flushing chemotherapy lines will not result in protocol deviation.

Extravasation of loncastuximab tesirine may be associated with local irritation, swelling, pain, or tissue damage. The IV infusion site should be monitored for signs of IV infiltration or drug extravasation, and patients should be instructed to report immediately any signs of IV infiltration or drug extravasation during or after the infusion. Suspected extravasation of loncastuximab tesirine should be managed according to institutional protocol for management of extravasation of cytotoxic chemotherapy. For patients who have a central line, administration of loncastuximab tesirine via this central line should be considered.

Idelalisib

Idelalisib is available as 100 mg and 150 mg oval-shaped tablets in a high-density polyethylene bottle with a polyester fiber coil, capped with a child-resistant closure. Each bottle contains 60 film-coated tablets and is to be dispensed only in original container.

If supplied through the study sufficient idelalisib will be dispensed until the next visit.

6.3 Study Treatment Assignment and Dosing

- Patients who are eligible will be randomized via Interactive Response Technology to either of the study treatment arms, loncastuximab tesirine or idelalisib in a 2:1 ratio. Loncastuximab Tesirine Arm: Administration of loncastuximab tesirine will be performed by the Investigator or a qualified designee. Patients will receive a 30 minutes IV infusion of loncastuximab tesirine on Day 1 of each cycle (150 µg/kg Q3W for 2 cycles, then 75 µg/kg Q3W for subsequent cycles).
Refer to [Section 6.4](#) for premedication and [Section 6.8](#) for supportive care.
- Idelalisib Arm: Patients will receive 150 mg idelalisib tablet orally BID. Please refer to [idelalisib prescribing information](#) or [idelalisib SmPC](#) for detailed instructions.

6.4 Premedication

Unless contraindicated, administer dexamethasone 4 mg orally BID, the day before loncastuximab tesirine administration (if possible), the day of loncastuximab tesirine administration (give at least 2 hours prior to administration when not given the day before; otherwise any time prior to administration), and the day after loncastuximab tesirine administration. Dexamethasone may be given IV if clinically indicated.

Patients who experience an infusion-related hypersensitivity reaction will receive the alternative premedication regimen specified in [Section 6.8.2](#) for more details.

6.5 Treatment Compliance

The Investigator or his/her designated and qualified representatives will administer/dispense the study treatments only to patients enrolled in the study in accordance with the protocol. Compliance will be verified by the study treatment administration information recorded in the electronic data capture (EDC).

Home administration of idelalisib will be documented in a patient diary, which will be reviewed by the Investigator or designee at each study visit.

6.6 Definition and Management of Overdose

An overdose is any dose of study drug administered to the patient that exceeds the maximum dose described in the protocol by 15% or more. Any overdose, with or without associated AEs, must be promptly reported to the Sponsor (see [Section 8.5.3](#)). There are no data available to determine what the effects of overdose of loncastuximab tesirine and idelalisib are and whether they can be reversed. Symptomatic treatment and standard supportive care measures for the management of any observed toxicity should be applied.

If feasible, a sample for pharmacokinetic (PK) analysis should be taken as close as possible to the overdose event.

6.7 Dose Delays and Modifications

6.7.1 Dose Delays and Modifications for Loncastuximab Tesirine and Idelalisib

The criteria and guidance for dose delay and dose modifications of loncastuximab tesirine and idelalisib are summarized in [Table 4](#) and [Table 5](#), respectively.

Table 4. Criteria for Dose Delay or Dose Modification of Loncastuximab Tesirine

Toxicity	Loncastuximab Tesirine
Grade ≥ 3 non-hematologic adverse events	
Hold until the toxicity resolves to Grade ≤ 1, (Grade 1 or baseline for peripheral neuropathy)If dosing is delayed by more than 3 weeks and the toxicity is considered at least possibly related to loncastuximab tesirine, then subsequent doses must be reduced by 50%. If the toxicity recurs, subsequent doses must be reduced by an additional 50%A maximum of 2 dose reductions are allowedNote: Patients who have a toxicity meeting the criteria for dose reduction following Cycle 2 will receive the protocol-specified dose of 75 $\mu\text{g}/\text{kg}$ for Cycle 3, i.e., they will not have an additional dose reduction for Cycle 3
Grade ≥ 2 edema, effusion	
Hold until the toxicity resolves to Grade ≤ 1If dosing is delayed by more than 3 weeks and the toxicity is considered at least possibly related to loncastuximab tesirine, then subsequent doses must be reduced by 50%. If the toxicity recurs, subsequent doses must be reduced by an additional 50%A maximum of 2 dose reductions are allowedNote: Patients who have a toxicity meeting the criteria for dose reduction following Cycle 2 will receive the protocol-specified dose of 75 $\mu\text{g}/\text{kg}$ for Cycle 3, i.e., they will not have an additional dose reduction for Cycle 3

Toxicity	Loncastuximab Tesirine
Grade ≥ 3 neutropenia or thrombocytopenia	
• Hold until toxicity resolves to Grade ≤ 2• If dosing is delayed by more than 3 weeks and the toxicity is considered at least possibly related to loncastuximab tesirine, then subsequent doses must be reduced by 50%. If the toxicity recurs, subsequent doses must be reduced by an additional 50%• A maximum of 2 dose reductions are allowed• Note: Patients who have a toxicity meeting the criteria for dose reduction following Cycle 2 will receive the protocol-specified dose of 75 $\mu\text{g}/\text{kg}$ for Cycle 3, i.e., they will not have an additional dose reduction for Cycle 3
Grade 4 infusion related reaction	
• Permanently discontinue loncastuximab tesirine
Hy's law (AST and/or ALT $> 3 \times \text{ULN}$ and bilirubin $> 2 \times \text{ULN}$)	
• Permanently discontinue loncastuximab tesirine. Hy's law defined as: AST and/or ALT $> 3 \times \text{ULN}$ and bilirubin $> 2 \times \text{ULN}$, and without initial findings of cholestasis (ALP activity $< 2 \times \text{ULN}$) and no other reason that could explain the combination of increased transaminases and serum total bilirubin, such as viral hepatitis A, B, or C, preexisting or acute liver disease, or another drug capable of causing the observed injury

Table 5. Criteria for Dose Delay or Dose Modification of Idelalisib

Toxicity	Idelalisib
Grade ≥ 2 symptomatic pneumonitis of any severity	Permanently discontinue idelalisib
Grade 2 increased ALT/AST/bilirubin or diarrhea	Maintain idelalisib dose. Monitor at least weekly until normal
Grade 3 increased ALT/AST/bilirubin or diarrhea	Withhold idelalisib. Monitor at least weekly until normal, then may resume idelalisib at 100 mg BID.
Grade 4 increased ALT/AST/bilirubin or diarrhea	Discontinue idelalisib permanently
Grade 3 neutropenia and/or thrombocytopenia	Maintain Idelalisib dose. Monitor ANC and/or platelet count at least weekly
Grade 4 neutropenia and/or thrombocytopenia	Withhold idelalisib. Monitor ANC and/or platelet count at least weekly. When neutropenia and thrombocytopenia are Grade 3 or less, may resume idelalisib at 100 mg BID
Grade ≥ 3 sepsis or pneumonia	Withhold idelalisib until infection has resolved.
Active CMV infection of any grade or viremia (positive PCR or antigen test)	Withhold idelalisib until the infection and viremia have resolved. If idelalisib is resumed, monitor by PCR or antigen for CMV reactivation at least monthly.
Suspected PJP infection of any grade.	Withhold idelalisib. Permanently discontinue idelalisib if PJP infection is confirmed.
Other Grade ≥ 3 non-hematologic toxicities	Withhold idelalisib until resolved, then may resume idelalisib at 100 mg BID. If the same grade ≥ 3 toxicity recurs after resuming idelalisib, permanently discontinue idelalisib
Anaphylaxis, Intestinal Perforation, Stevens-Johnson syndrome (SJS) and toxic epidermal necrolysis (TEN)	Permanently discontinue idelalisib

Abbreviations: ALT=alanine aminotransferase; ANC= Absolute neutrophil count; AST=aspartate aminotransferase; BID=twice daily; CMV=cytomegalovirus; PCR=polymerase chain reaction; PJP=Pneumocystis jirovecii pneumonia.

Reference: [Idelalisib® Prescribing Information](#) For additional information on management of toxicities, please refer to the [Investigator Brochure for loncastuximab tesirine](#) and to the [prescribing information](#) or [SmPC](#) for idelalisib.

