5.2 Exclusion Criteria

1. Previous treatment with loncastuximab tesirine.
2. Previous treatment with idelalisib.
3. History of hypersensitivity to any of the excipients of loncastuximab tesirine or idelalisib.
4. Follicular lymphoma which has transformed to DLBCL or other aggressive lymphomas.
5. Requires treatment or prophylaxis with a strong cytochrome P450 (CYP) 3A inhibitor, inducer, or sensitive substrate.
6. History of or ongoing drug-induced pneumonitis.
7. History of or ongoing inflammatory bowel disease.
8. Any condition that could interfere with the absorption or metabolism of idelalisib including malabsorption syndrome, disease significantly affecting gastrointestinal function, or resection of the stomach or small bowel.

9. Active second primary malignancy other than non-melanoma skin cancers, non-metastatic prostate cancer, in situ cervical cancer, ductal or lobular carcinoma in situ of the breast, or other malignancy that the Sponsor's medical monitor and Investigator agree and document should not be exclusionary.
10. Autologous transplant within 30 days prior to start of study treatment (C1D1).
11. Allogenic transplant within 60 days prior to start of study treatment (C1D1).
12. Active graft-versus-host disease.
13. Post-transplantation lymphoproliferative disorders.
14. Human immunodeficiency virus (HIV) seropositive with any of the following:
 - a. CD4+ T-cell counts <350 cells/ μ L.
 - b. Acquired immuno-deficiency syndrome (AIDS)-defining opportunistic infection within 12 months prior to screening.
 - c. Not on anti-retroviral therapy, or on anti-retroviral therapy for < 4 weeks at the time of screening.
 - d. HIV viral load \geq 400 copies/mL.
15. Serologic evidence of chronic hepatitis B infection and unable or unwilling to receive standard prophylactic anti-viral therapy or with detectable hepatitis B virus (HBV) viral load.
16. Serologic evidence of hepatitis C infection without completion of curative treatment or with detectable hepatitis C virus (HCV) viral load.
17. History of Stevens-Johnson syndrome or toxic epidermal necrolysis.
18. Lymphoma with active central nervous system involvement, including leptomeningeal disease.
19. Clinically significant third space fluid accumulation (i.e., ascites requiring drainage or pleural effusion that is either requiring drainage or associated with shortness of breath).
20. Breastfeeding or pregnant.

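### Table 4 has no permanent-stop rule for SJS/TEN on loncastuximab tesirine, so a Grade ≥3 case falls under a hold-and-resume rule, although Table 5 stops idelalisib for the same event

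*Combined protocol and SAP*

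**What the plan says.** Section 6.7.1, Table 4 (loncastuximab tesirine) has five rows. Two end in permanent discontinuation: Grade 4 infusion related reaction and Hy's law. No row names SJS, TEN or any skin event. The row for Grade ≥3 non-hematologic events starts "Hold until the toxicity resolves to Grade ≤ 1, (Grade 1 or baseline for peripheral neuropathy" and requires a 50% reduction only under this condition: "If dosing is delayed by more than 3 weeks and the toxicity is considered at least possibly related to loncastuximab tesirine".

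Section 6.7.1, Table 5 (idelalisib) has a permanent-discontinuation row for "Anaphylaxis, Intestinal Perforation, Stevens-Johnson syndrome (SJS) and toxic epidermal necrolysis (TEN".

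Section 5.2, exclusion criterion 17 bars from either arm any patient with "History of Stevens-Johnson syndrome or toxic epidermal necrolysis".

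Section 5.5.1 introduces its mandatory list with "A patient must discontinue from the study drug for any of the following reasons". The list contains pregnancy and death. Adverse events and physician decision are on the separate list of reasons for which a patient may be discontinued.

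Section 6.3 sets the dose at 150 µg/kg for Cycles 1 and 2 and 75 µg/kg afterwards. Section 4.2.3 sets the loncastuximab tesirine cycle at 21 days.

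**The concern.** The protocol treats SJS/TEN as disqualifying in two places, at entry and during idelalisib treatment. For a patient who develops it on the experimental drug, the dose table has no stop, and the row that covers the event by grade tells the site to hold and then resume. A site could redose such a patient, possibly at the full starting dose, and remain compliant. Yet the same history would have excluded that patient at screening.

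What is at stake is the safety of an individual patient with a life-threatening reaction. The primary comparison, its power and its type I error are not involved.

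**Working it through.** The plan gives no figure to reproduce. The check sets the provisions side by side and then does the day and dose arithmetic.

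**Which rule covers the event**

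| Provision | Effect for SJS/TEN on loncastuximab tesirine |
|---|---|
| Table 4, Grade 4 infusion reaction and Hy's law rows (2 of 5 rows) | Do not cover it |
| Table 4, Grade ≥3 non-hematologic row | Covers it by grade: hold to Grade ≤1, then resume |
| 5.5.1 mandatory list | Pregnancy and death only |
| 5.5.1 permissive list; unacceptable toxicity in 4.2.3 | The investigator may stop; unacceptable toxicity is not defined |
| 6.8.3 skin toxicity | For blistering rash, topical care and tests for other blistering disorders; steroids for clinically significant toxicity and a dermatology consult at Grade ≥2 are to be considered; no mention of SJS/TEN or of stopping |
| 4.3 Grade 4 skin rule | Pauses enrollment; needs more than 2 patients and more than 5% incidence on this drug, so one case cannot trigger it; does not govern an individual's dosing |

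The cap in Table 4 ("A maximum of 2 dose reductions are allowed") does not close the gap. It limits reductions and is not worded as a stop, and a first event uses at most one reduction.

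**Dose after a Cycle 1 event**

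Inputs: C1D1 is Day 1, the cycle is 21 days, and the delay is counted from the scheduled dose (an assumption, since Table 4 does not define the starting point).

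- Cycle 2 due: 1 + 21 = Day 22.
- Last day with a delay of no more than 3 weeks: 22 + 21 = Day 43.
- Days available to reach Grade ≤1 without triggering a reduction: 43 − onset day. Onset on Day 1 gives 42 days, Day 10 gives 33 and Day 21 gives 22.

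The branches of the row are then:

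- Delay of 21 days or less, related or not: 150 µg/kg.
- Delay over 21 days, judged unrelated: 150 µg/kg.
- Delay over 21 days, at least possibly related: 150 × 0.5 = 75 µg/kg.

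**Later events**

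After a Cycle 2 event, Cycle 3 is 75 µg/kg in every branch, because the table's note waives a further reduction. After an event in a later cycle, a delay of 3 weeks or less leaves the dose unchanged. No branch for a first event ends in a stop.

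**Grade assumption**

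The documents do not state the CTCAE grade of SJS/TEN. The check assumes Grade ≥3. A case graded lower would not meet even this row's hold, which is why the fix applies to any grade.

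**The case against.** The best defense is that the two tables are drug-specific. The note under Table 5 cites the idelalisib prescribing information as its source, and the SJS/TEN row sits among other idelalisib risks. Exclusion 17 has to apply to both arms because eligibility comes before randomization. Exclusion 8 likewise concerns only idelalisib absorption and metabolism and still binds everyone. This stands. A reader might infer that the exclusion shows the sponsor regards SJS/TEN as a known risk of loncastuximab tesirine. The documents do not support that, and they report no such case.

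A reader might also infer that SJS/TEN is the only, or almost the only, place where the written stopping rules differ by arm. That is wrong. Table 5 also stops idelalisib for pneumonitis, Grade 4 ALT/AST/bilirubin or diarrhea, confirmed PJP, anaphylaxis, intestinal perforation and recurrence of another Grade ≥3 non-hematologic toxicity. Table 4 alone stops for Hy's law. Asymmetry by itself is therefore no evidence of an oversight.

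A third point is that investigators have discretion. Section 4.2.3 ends permission to treat at unacceptable toxicity, and most investigators would stop. Sections 6.7.1 and 6.8 also refer them to the Investigator's Brochure, which may say more. The weak force of the 5.5.1 list is also conceded: disease progression is only a permissive reason there, and the Hy's law stop binds through Table 4 without appearing on the mandatory list.

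These points limit the finding but do not remove it. The concern does not depend on the asymmetry. A row in the controlling table covers the event and directs hold-and-resume, and the text that could override it leaves the choice to judgment. Table 4 spells out a stop for Hy's law without relying on the Brochure, and SJS/TEN merits the same.

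**Conclusion.** The gap is real and narrow. Table 4 contains no permanent stop for SJS/TEN, and its general row permits redosing. After a Cycle 1 event the dose may be 150 µg/kg if the delay is 3 weeks or less (to Day 43) or the event is judged unrelated, and 75 µg/kg if the event is related and the delay is longer. It would be too strong to say that the protocol directs sites to redose these patients. It permits redosing, and the investigator may stop at any time.

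The number of patients affected cannot be estimated. The documents give no SJS/TEN rate for this drug. A rate assumed from elsewhere would give the chance of a case, not the chance that a case resolves to Grade ≤1 and is then redosed. The argument for acting is the gravity of the event set against a very small cost.

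The conclusion assumes that SJS/TEN would be graded 3 or higher and that delay is counted from the scheduled dose. It covers only the text available: the Investigator's Brochure could not be checked. This is a cheap safety improvement that should be made, and it does not threaten the validity of the trial.

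**What to change.** Add one row to Table 4: *SJS or TEN, any grade: hold if suspected; permanently discontinue loncastuximab tesirine if confirmed.*

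Optionally, add to the mandatory list in 5.5.1 a cross-reference to the permanent-discontinuation criteria of Tables 4 and 5, so that the two sections agree.

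The cost is one table row, and if wanted one line in 5.5.1, at the next amendment. A patient with confirmed SJS/TEN loses the option of rechallenge, which Table 5 already rules out for idelalisib. Sample size, alpha and the primary analysis are unchanged.
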